6.4 Withdrawal criteria

Subjects are free to withdraw from the study at any time, without prejudice to their continued care.

Subjects **must** be withdrawn from the study if any of the following events occurs:

- The subject is unable to attain at least the minimum Maintenance Period target dose (Table 7-3).
- The subject requires a subsequent dose increase after dose reduction during the Maintenance Period or the subject requires more than 1 dose reduction during the Maintenance Period.
- Subject develops a second- or third-degree AV block.
- The subject becomes pregnant, as evidenced by a positive pregnancy test.
- The sponsor or a regulatory agency requests withdrawal of the subject.
- The subject is unwilling or unable to continue and withdraws consent.
- In the case of liver function test (LFT) results of transaminases (AST and/or ALT) $\geq 3 \times \text{ULN}$ to $< 5 \times \text{ULN}$ and total bilirubin $\geq 2 \times \text{ULN}$ or transaminases (AST and/or ALT) $\geq 5 \times \text{ULN}$, LCM must be immediately discontinued and the subject withdrawn from the study. The LFTs will be repeated as soon as possible, and in no case more than 1 week later.
- Subject ≥ 6 years of age has actual suicidal ideation as indicated by a positive response ("Yes") to either Question 4 or Question 5 of the "Since Last Visit" version of the C-SSRS. The subject should be referred immediately to a Mental Healthcare Professional and must be withdrawn from the study.

Subjects **may** be withdrawn from the study if any of the following events occur:

- The subject requires a medication that is not permitted.
- The subject requires a modification to concomitant AED dose(s) during the study (see Section 7.8).
- The subject is unable to manage the completion of the diary, demonstrates a questionable diary, or is noncompliant with the study procedures or medications in the opinion of the investigator.
- An episode of status epilepticus, a prolongation of seizure duration, a worsening of seizure frequency, or emergence of a new seizure type considered by the investigator to require intervention.
- Subject develops a clinically relevant change in medical condition (or ECG or laboratory parameter) as determined by the investigator, and the investigator feels it is in the interest of the subject to withdraw.
- Subject develops an intolerable AE during the course of the study.

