9.3.1 Seizure variables

Subjects will keep a diary to record daily seizure activity from Visit 1 until the end of study participation. Efficacy and safety variables will be assessed using the seizure count information recorded on the subject diaries. Subjects should be reminded that diaries must include daily entries even if no seizures have occurred. The subject should be reminded to bring the diary to each clinic visit.

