13.1.4 Full Analysis Set

The Full Analysis Set (FAS) is a subset of the SS consisting of all subjects with at least 1 seizure diary assessment during the Treatment Period. This population will serve as the primary population for assessing efficacy endpoints.

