13.3 Planned efficacy analyses

13.3.1 Analysis of the primary efficacy variable

The primary efficacy variable, time to second PGTC seizure during the 24-week Treatment Period, will be evaluated using a Cox proportional hazards regression model (Cox, 1972), with an effect for treatment, stratifying for the subjects' Baseline PGTC seizure frequency (≤ 2 per 28 days vs > 2 per 28 days in the 16 weeks prior to randomization) and age at informed consent (≥ 4 to < 12 years of age, ≥ 12 to < 18 years of age vs ≥ 18 years of age). Pooling strategies for strata with a low number of events will be defined in the SAP prior to unblinding. Subjects who prematurely discontinue from the study will be censored on the date of last dose of study drug during the Treatment Period.

Additionally, a Kaplan-Meier (KM) plot for time to second PGTC seizure as well as the KM estimate for the median time to second PGTC seizure will be provided. This analysis will be performed using the FAS population.

Testing for the primary endpoint will be done at the 5% level (2-sided). A gatekeeping strategy (Marcus et al, 1996) will be used to test the key secondary efficacy variable provided that the primary endpoint is statistically significant (See Section 13.3.2 for additional details). No additional adjustments for multiplicity are required as all additional inferences will be hypothesis-generating only.

The following additional sensitivity analyses on the primary efficacy endpoint will be conducted in order to assess the effect of dropouts, protocol deviations, and operational bias on the primary endpoint:

- Repeat the primary analysis using the PPS.
- Repeat the primary analysis using the FAS, except all subjects who prematurely discontinue due to lack of efficacy, consent withdrawn, or lost to follow-up will be analyzed as treatment failures (ie, events at the time of discontinuation).
- Repeat the primary analysis using the FAS, except all subjects who prematurely discontinue due to lack of efficacy or AEs only will be analyzed as treatment failures.
- Repeat the primary analysis using the FAS, comparing the event rates at each interim analysis to examine possible operational bias due to unblinding.

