13.3.2 Secondary efficacy analyses

13.3.2.1 Key secondary efficacy variable

Analysis of the key secondary efficacy variable, seizure freedom for PGTC seizures for the 24-week Treatment Period, will be analyzed in the same manner as the primary endpoint using the FAS. The percentage of seizure-free subjects at 24 weeks will be estimated from the KM estimates of time to first seizure using 2-sided 95% confidence intervals. A gatekeeping strategy will be employed to control the Type I error (Marcus et al, 1976). If the primary endpoint is statistically significant at the 5% level, then the key secondary efficacy endpoint will also be assessed at the 5% significance level. If the primary endpoint fails to reach statistical significance, then the key secondary efficacy endpoint will be exploratory only.

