13.6 Handling of dropouts or missing data

All data will be used to the maximum possible extent, but without any imputations for missing data for any parameter, unless otherwise specified in the SAP. Sections 13.3.1 and 13.3.2 provide additional sensitivity analyses for the primary efficacy and key secondary efficacy endpoints, respectively.

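### Premature discontinuers are censored at last dose with no diary condition, so for anyone whose diary ends earlier the undocumented days count as event-free; the effect is small

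*Protocol*

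**What the plan says.** Section 13.3.1 fixes the censoring date for the primary endpoint, time to second PGTC seizure, without any condition: "Subjects who prematurely discontinue from the study will be censored on the date of last dose of study drug during the Treatment Period". The same paragraph leaves stratum pooling to the SAP but does not leave the censoring date to it.

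Section 13.3.2.1 says the key secondary endpoint "will be analyzed in the same manner as the primary endpoint using the FAS", and adds: "The percentage of seizure-free subjects at 24 weeks will be estimated from the KM estimates of time to first seizure". The last-dose rule therefore reaches both tested endpoints.

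On the data source, section 9.3.1 says: "Efficacy and safety variables will be assessed using the seizure count information recorded on the subject diaries". It also says that "diaries must include daily entries even if no seizures have occurred". Section 6.4 lists as a possible reason for withdrawal: "The subject is unable to manage the completion of the diary, demonstrates a questionable diary". The Full Analysis Set (13.1.4) asks only for "all subjects with at least 1 seizure diary assessment during the Treatment Period". Section 13.6 says data will be used "without any imputations for missing data for any parameter, unless otherwise specified in the SAP".

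**The concern.** The follow-up clock and the observation window rest on different records. The last dose comes from dosing and drug accountability records; seizures come from the diary. Because a seizure-free day also needs an entry, a day without one is missing, not seizure-free. A subject who keeps dosing after the diary stops stays at risk on days when no event can be seen. That amounts to imputing seizure freedom, which sits badly with 13.6.

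Within an arm the error has one sign: it adds event-free time. What is at stake is a slightly high 24-week seizure-freedom estimate in each arm and, if such gaps are commoner in one arm, a small shift in the treatment comparison.

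**Working it through.** **1. The plan's own figure.** Section 13.8 gives 125 events for 90% power at a hazard ratio (HR) of 0.56, two-sided 5%, with 1:1 allocation (5.1). Schoenfeld: 4 × (1.960 + 1.282)² / (ln 0.56)² = 125.02, and power at 125 events is 0.89996. The figure reproduces, and this point does not affect it.

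**2. Mechanism.** The Kaplan-Meier estimate multiplies factors 1 − d/n over days, with d events among n at risk. An undocumented day adds to n and can never add to d. Each affected factor is too close to 1, so estimated seizure freedom rises. In the Cox model the same days dilute the hazard of the arm they fall in.

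**3. Can the gap occur?** It needs a diary that ends before the last dose. Diary failure is a foreseen withdrawal reason (6.4). From Week 8 the clinic visits at which diaries are returned are 4 weeks apart (8.2.3), so a subject lost to follow-up may leave up to about 4 weeks unreturned.

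**4. Do the planned sensitivity analyses remove it?** Those in 13.3.1 use the Per Protocol Set, recode some discontinuers as events, or compare event rates at the interim analyses. None moves the censoring date to the last diary day. Section 13.6 says 13.3.2 provides sensitivity analyses for the key secondary endpoint, but 13.3.2 contains none.

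**5. Size, both endpoints.** From 13.8: placebo survival 25.4%, HR 0.56, overall dropout 15%. Assumed: 25.4% applies at Week 24, exponential times, first seizure uniform before the second, the same diary gap for every dropout, and the splits of dropout by arm. Simulation with 400,000 subjects per arm:

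| Gap; dropout LCM/placebo | HR, last dose | HR, last diary day | LCM seizure freedom, last dose | LCM seizure freedom, last diary day |
|---|---|---|---|---|
| 28 days; 15%/15% | 0.559 | 0.558 | 22.1% | 21.2% |
| 28 days; 20%/10% | 0.552 | 0.562 | 22.4% | 21.0% |
| 28 days; 10%/20% | 0.570 | 0.558 | not tabulated | not tabulated |
| 7 days; 20%/10% | 0.558 | 0.561 | 21.5% | 21.2% |

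At 28 days and 15%/15%, placebo seizure freedom reads 9.3% instead of 8.7%. The HR shifts in the two unequal 28-day splits are 0.552 − 0.562 = −0.010 and 0.570 − 0.558 = +0.012.

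**6. Size over a range of seizure-free rates.** Assumed true 24-week seizure freedom 10% to 25% on placebo and 20% to 40% on LCM, 300,000 subjects per arm, 15% dropout in both arms. Inflation per arm, in percentage points:

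- 7-day gap: 0.16 to 0.25
- 14-day gap: 0.33 to 0.49
- 28-day gap: 0.70 to 0.97
- 56-day gap: 1.56 to 1.94

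With a 28-day gap, 20% LCM/10% placebo dropout moves the LCM-minus-placebo difference by +0.71 to +0.81 points; the reverse split moves it by −0.36 to −0.70. With a 7-day gap, the inflation over equal and 20/10 splits is 0.10 to 0.33 points.

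**7. Full Analysis Set check.** With a 28-day gap, a subject who drops out before day 28 has no Treatment Period diary and leaves the Full Analysis Set. With these subjects removed, the rise in LCM seizure freedom at 15%/15% is about 0.8 points, the HR is still unchanged, and the 20/10 splits still move it by about 0.01 either way.

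**8. Against sampling error.** The standard error of a 21% estimate with 100 subjects is at least √(0.21 × 0.79 / 100) = 4.1 points. With 125 events the standard error of the log HR is √(4/125) = 0.179; a shift from 0.562 to 0.552 is ln(0.562/0.552) = 0.018, about 0.1 standard error.

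Censoring at the last diary day recovered the true values within simulation error in every case.

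**The case against.** The strongest reply is that the protocol's procedures work against the gap. Diary completion is checked at every clinic visit and telephone contact (7.7), and these are weekly in the first 6 weeks. Drug and diary come back at the same visits. Discontinuers are to complete an ET Visit and a taper (7.2.4), and the last diary is returned at the End of Taper Visit (Table 5-3, note d). For a discontinuer who follows this, the diary outlasts the last Treatment Period dose and the problem does not arise. That stands: it limits the point to discontinuers who stop the diary while still dosing or whose last diary is never recovered. The protocol does not say how many these will be.

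A second reply is that days without diary entries are SAP matter. This stands only in part. The SAP, which was not available for this check, may add a diary rule, and no sentence in the protocol declares undocumented days seizure-free. But the protocol itself fixes the censoring date, and applying it as written has that result.

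A reader might infer more: that the rule favours lacosamide, or always inflates most in the arm with more dropouts. The documents do not support this. Section 13.8 gives 15% dropout with no split by arm; the reverse split moves the HR against lacosamide; and the statement about the arm with more dropouts assumes similar gaps in both arms.

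**Conclusion.** The point holds as a minor defect in a stated rule. For discontinuers whose diary ends before the last dose, last-dose censoring counts unobserved days as event-free in the primary and key secondary analyses, and no planned analysis corrects this. It can slightly raise 24-week seizure freedom in both arms. It does not move the HR when dropout and gaps are equal between arms, and moves it by about 0.01 in either direction under 20/10 splits.

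The sizes rest on assumed gap lengths, assumed dropout by arm and exponential times. A 28-day gap for every dropout is an upper case given the visit spacing; shorter or rarer gaps shrink the effect. None of this threatens the primary conclusion. The reason to change the rule is that follow-up should end where observation ends, and that this is best settled before unblinding.

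**What to change.** In 13.3.1, and so in 13.3.2.1, censor premature discontinuers at the earlier of the last dose in the Treatment Period and the last day with a diary entry. Keep censoring at last dose as a sensitivity analysis for both endpoints, and carry the same wording into the SAP.

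The cost is one sentence and the loss of undocumented days for some dropouts. The change does not deal with informative dropout or with isolated missing days before the last entry.

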13.3.2 Secondary efficacy analyses

13.3.2.1 Key secondary efficacy variable

Analysis of the key secondary efficacy variable, seizure freedom for PGTC seizures for the 24-week Treatment Period, will be analyzed in the same manner as the primary endpoint using the FAS. The percentage of seizure-free subjects at 24 weeks will be estimated from the KM estimates of time to first seizure using 2-sided 95% confidence intervals. A gatekeeping strategy will be employed to control the Type I error (Marcus et al, 1976). If the primary endpoint is statistically significant at the 5% level, then the key secondary efficacy endpoint will also be assessed at the 5% significance level. If the primary endpoint fails to reach statistical significance, then the key secondary efficacy endpoint will be exploratory only.

13.3.2.2 Other secondary efficacy variables

All safety analyses will be described in the SAP. Analyses of the other secondary efficacy variables will be performed using the FAS and will be descriptive in manner only. Any p-values or confidence limits provided other than those for the primary analysis of the primary variable (as described in Section 13.3.1) and the analysis of the key secondary efficacy variable (as described in Section 13.3.2.1) will be exploratory only.

Time to the first PGTC seizure for the Treatment Period will be analyzed in the same manner as the primary endpoint using the FAS.

Further approaches for the analysis of the secondary variable will be described in a detailed SAP.

13.3.3 Other efficacy analysis

Analysis of the other efficacy endpoints listed in Section 4.1.3 of the protocol will be presented descriptively. Additional details will be provided in the SAP.

13.4 Planned safety and other analyses

Analyses of other variables, eg, safety or plasma concentration data, will be descriptive in manner only. Lacosamide plasma concentrations will be summarized and evaluated by population PK; details will be provided in a separate analysis plan.

The incidence and frequency of TEAEs will be summarized for each treatment group and study period. The incidence of SAEs and TEAEs leading to premature discontinuation from study drug will also be summarized for each treatment group and study period. Additional summaries will be provided by maximum intensity and relationship to study drug. All tables for AEs will be displayed by MedDRA® primary System Organ Class and Preferred Term. Further details on the analysis of AE data will be given in the SAP.

Observed values and changes from Baseline in vital signs, body weight, continuous laboratory parameters, and 12-lead ECG measurements will be summarized using continuous descriptive statistics. The number and percentage of subjects in each category will be summarized for the categorical outcomes. Shift tables summarizing the number and percentage of subjects having a different status (eg, abnormal laboratory result) post-Baseline compared to Baseline will be provided.

Incidence of new seizure types, and increase in absence seizure days per 28 days or myoclonic seizure days per 28 days during the Treatment Period will be summarized for each treatment group.

13.5 Handling of protocol deviations

Important protocol deviations are deviations from the protocol which potentially could have a meaningful impact on outcomes for an individual subject. The criteria for identifying important protocol deviations and the classification of important protocol deviations will be defined within the project Data Cleaning Plan (DCP). To the extent feasible, rules for identifying protocol deviations will be defined without review of the data and without consideration of the frequency of occurrence of such deviations. Whenever possible, criteria for identifying important protocol deviations will be implemented algorithmically to ensure consistency in the classification of important protocol deviations across all subjects.

Important protocol deviations will be reviewed in a blinded manner a part of the ongoing data cleaning process prior to database lock to confirm exclusion from analysis sets.

13.6 Handling of dropouts or missing data

All data will be used to the maximum possible extent, but without any imputations for missing data for any parameter, unless otherwise specified in the SAP. Sections 13.3.1 and 13.3.2 provide additional sensitivity analyses for the primary efficacy and key secondary efficacy endpoints, respectively.

13.7 Planned interim analysis and data monitoring

Some AEDs with sodium channel blocking properties can exacerbate some generalized seizure types, such as absence and myoclonic seizures. To enhance safety monitoring, 3 interim analyses are planned when 25%, 50%, and 75% of subjects experience an event (31, 62, and 93 events, respectively) or 24 weeks after 50, 100, and 150 subjects have been randomized, respectively, whichever comes first. An event is defined as the occurrence of the second PGTC seizure during the Treatment Period.

Three interim analyses for safety will be performed by the IDMC with a single futility assessment planned at the second interim analysis. The IDMC will oversee the safety of the study by reviewing safety data periodically. Details will be provided in an IDMC charter. Both safety and futility will be assessed in a manner that ensures that blinding is not compromised for individuals involved with operational aspects of the study, or individuals involved with the planning and conduct of the final statistical analyses. Analysis of the primary endpoint (time to second PGTC seizure) will only be examined at the planned futility assessment; an unblinded, descriptive review of safety, PGTC seizure frequency, and changes in days with absence and/or myoclonic seizures will be provided for all IDMC meetings.

Additional details, including the methods used for assessing futility, will be provided in the interim SAP. Neither futility or the IDMC safety assessments are expected to have any impact on the Type 1 error as there will be no stopping rule for success in place; however, the significance level will be set using a Haybittle-Peto boundary at $\alpha=0.0001$ so as not to require any adjustment to the overall alpha level for the final analysis.

The IDMC will consist of 3 voting members, none of whom will be involved with the conduct of the study, either by management or participation. In addition, there will be an independent reporting team, consisting of an independent statistician and statistical programmers, who will be completely independent from the blinded reporting team. The blinded reporting team will be responsible for all operational aspects of the study, including routine monitoring and cleaning of the data, programming, and quality control (QC) of all analyses defined in the interim SAP on blinded data.

The blinded study team will actively monitor the number of events in the study. Once the required number of events (or subjects) has been met and the blinded reporting team has completed the QC of the IDMC tables, figures, and listings (TFLs), the programs will be passed to the independent reporting team. The independent statistician will request unblinded treatment codes from the IRT randomization coordinator and the TFLs will be re-run and QC'd using the actual treatment codes. Additional TFLs or ad hoc analyses can be requested by the IDMC based on their data review.

Any changes to predefined TFLs or new requests will be handled by the independent reporting team.

The actual randomization codes and the unblinded outputs will be stored in a secure location which will be accessible only to the independent reporting team. A secure, restricted-access directory will hold electronic copies of documents such as meeting minutes, interim reports, emails, and periodic data deliveries. Only the independent reporting team will have access to this secure location.

13.8 Determination of sample size

Observing 125 events (subjects who had a second PGTC seizure during the 24-week Treatment Period) will provide 90% power to observe a hazard ratio of 0.56 at the 2-sided 5% level, assuming a dropout rate of 15%. The observed hazard ratio was based on a 25.4% survival rate for placebo and 48.2% for lamotrigine from a previous study comparing lamotrigine and placebo (French et al, 2007). The observed hazard ratio in the lamotrigine study was 0.533; however, in order to account for the possibility of an increased placebo response, as has been documented in recent clinical studies of AEDs, the hazard ratio was increased by 5% to 0.56 for estimating a sample size for this study. The rationale for the increase in the hazard ratio included the following considerations: different active compounds (LCM and lamotrigine) and a choice of time to second seizure as the primary efficacy endpoint (in the lamotrigine study, percent change in PGTC seizure frequency was the primary endpoint) (see rationale for second PGTC seizure in Section 5.4.2).

This is an event-driven study. Enrollment in the study will continue up to 125 events occurring or a maximum of 250 subjects randomized, whichever comes first.

